10.7 Reporting Process

Adverse events may be submitted on FDA Form 3500A, the HICCC DSMC Serious Adverse Event Reporting Form, or in a narrative format. If supplied as in a narrative format, the minimum information to be supplied is noted above at the beginning of section 10.5.

SAEs must be recorded on the HICCC DSMC SAE Report Form; pregnancies on a Pregnancy Surveillance Form (electronic or paper forms). These forms are to be transmitted via email or confirmed facsimile (fax) transmission to:

SAE Email Address: [contact]

- **SAE [contact]

For studies capturing SAEs through electronic data capture, electronic submission is the required method for reporting. In the event the electronic system is unavailable for transmission, paper forms must be used and submitted immediately. When paper forms are used, the original paper forms are to remain on site.

SAE Telephone Contact (required for SAE and pregnancy reporting): Refer to Contact Information list.

If only limited information is initially available, follow-up reports are required. (Note: Follow-up SAE reports must include the same investigator term[s] initially reported.)

If an ongoing SAE changes in its intensity or relationship to study drug or if new information becomes available, the SAE report must be updated and submitted within 24 hours to BMS (or designee) using the same procedure used for transmitting the initial SAE report.

All SAEs must be followed to resolution or stabilization.

A SUSAR (Suspected, Unexpected Serious Adverse Reaction) is a subset of SAEs and will be reported to the appropriate regulatory authorities and investigators following local guidelines and requirements.

10.8 Pregnancy

If, following initiation of the study drug, it is subsequently discovered that a study participant is

pregnant or may have been pregnant at the time of study exposure, including during at approximately 5 half-lives after product administration, the investigator must immediately notify BMS of this event and complete and forward a Pregnancy Surveillance Form to BMS Designee within 24 hours of awareness of the event and in accordance with SAE reporting procedures described in Section 10.6.

Follow-up information regarding the course of the pregnancy, including perinatal and neonatal outcome and, where applicable, offspring information, must be reported on the Pregnancy Surveillance Form.

Any pregnancy that occurs in a female partner of a male study participant should be reported to BMS. Information on this pregnancy will be collected on the Pregnancy Surveillance Form.

10.9 Overdose

An overdose is defined as the accidental or intentional administration of any dose of a product that is considered both excessive and medically important. All occurrences of overdose must be reported as an SAE (see Section 10.6 for reporting details).

10.10 Potential Drug Induced Liver Injury (DILI)

Wherever possible, timely confirmation of initial liver-related laboratory abnormalities should occur prior to the reporting of a potential DILI event. All occurrences of potential DILIs, meeting the defined criteria, must be reported as SAEs (see Section 10.6 for reporting details).

Potential drug induced liver injury is defined as:

1. AT (ALT or AST) elevation $> 3 \times \text{ULN}$

AND

2. Total bilirubin $> 2 \times \text{ULN}$, without initial findings of cholestasis (elevated serum alkaline phosphatase),

AND

3. No other immediately apparent possible causes of AT elevation and hyperbilirubinemia including, but not limited to, viral hepatitis, pre-existing chronic or acute liver disease, or the administration of other drug(s) known to be hepatotoxic.

10.11 Other Safety Considerations

Any significant worsening noted during interim or final physical examinations, electrocardiogram, x-ray filming, any other potential safety assessment required or not required by protocol should also be recorded as a nonserious or serious AE, as appropriate, and reported accordingly.

11 PHARMACEUTICAL INFORMATION

Study Drugs

11.1 Description

Investigational Product

In this protocol, the investigational product is nivolumab (Opdivo®).

Nivolumab (also referred to as Opdivo®) is a human monoclonal antibody (HuMAb; immunoglobulin G4 [IgG4]-S228P) that targets the PD-1 cluster of differentiation 279 (CD279) cell surface membrane receptor. PD-1 is a negative regulatory molecule expressed by activated T and B lymphocytes.²⁴ Binding of PD-1 to its ligands, PD-L1 and PD-L2, results in the down-regulation of lymphocyte activation. Inhibition of the interaction between PD-1 and its ligands promotes immune responses and antigen-specific T-cell responses to both foreign antigens as well as self-antigens. Nivolumab is expressed in Chinese hamster ovary cells and is produced using standard mammalian cell cultivation and chromatographic purification technologies. The clinical study product is a sterile solution for parenteral administration. Nivolumab is being investigated both as monotherapy and in combination with chemotherapy, targeted therapies, and other immunotherapies, in an array of solid and hematologic malignancies.

Non-investigational Product

None.

11.2 Treatment Regimen

Nivolumab Dose and Schedule

Participants should receive nivolumab at a dose of 240 mg as a 30-minute (\pm 7 minutes) infusion on Day 1 of each treatment cycle for the first 8 cycles until progression, unacceptable toxicity, withdrawal of consent, or the study ends, whichever occurs first. Participants should begin study treatment within 3 calendar days of treatment assignment. Beginning with Cycle 9, participants should receive nivolumab at a dose of 480 mg as a 30-minute (\pm 7 minutes) infusion until progression, unacceptable toxicity, withdrawal of consent, or the study ends, whichever occurs first.

There will be no dose escalations or reductions of nivolumab allowed. Participants may be dosed no less than 12 days from the previous dose. For Q4W dosing cycles, participants may be dosed within a \pm 3-day window. Premedications are not recommended for the first dose of nivolumab.

Participants should be carefully monitored for infusion reactions during nivolumab administration. If an acute infusion reaction is noted, participants should be managed according to Section 8.2.

Doses of nivolumab may be interrupted, delayed, or discontinued depending on how well the participant tolerates the treatment. Dosing visits are not skipped, only delayed.

Information regarding infusion details for nivolumab can be found in the Investigator Brochure.

Nivolumab Treatment Beyond Progression

Evidence indicates a minority of participants treated with immunotherapy may derive clinical benefit despite initial evidence of PD,²⁹ for example, due to inflammatory reaction simulating progression (“tumor flare” or pseudoprogression). Pseudoprogression is well described in neuro-oncology, and refers to radiographic enlargement of tumor lesions that would be interpreted as disease progression by conventional response criteria, but upon histologic examination reveals necrosis and/or inflammation (treatment effect) and not disease progression.²⁹

A similar phenomenon has been observed in various tumors when treated with immunotherapeutic agents, in which transient enlargement of lesions or appearance of new lesions is attributable to the influx of immune cells. These potential immune treatment effects complicate the evaluation of response and may lead to premature discontinuation of therapy. Furthermore, the time period to pseudoprogression or tumor flare with different immune therapies varies in different malignancies.

Participants treated with nivolumab will be permitted to continue nivolumab treatment beyond initial progressive disease, assessed by the investigator, as long as they meet the following criteria:

- Investigator-assessed clinical benefit
- Tolerance of study drug
- Treatment beyond progression will not delay an imminent intervention to prevent serious complications of disease progression (eg, severe symptoms due to brain mass effect)
- Participant provides written informed consent prior to receiving additional nivolumab treatment

All other elements of the main consent including description of reasonably foreseeable risks or discomforts, or other alternative treatment options will still apply.

A radiographic assessment/scan should be performed within 8 weeks of initial investigator-assessed progression to determine whether there has been a decrease in the tumor size or continued PD. The assessment of clinical benefit should be balanced by clinical judgment as to whether the participant is clinically deteriorating and unlikely to receive any benefit from continued treatment with nivolumab.

If the investigator considers that the nivolumab participant continues to achieve clinical benefit by continuing treatment, the participant should remain on the trial and continue to receive monitoring according to the time and events schedule in Section 12.2.

If at the radiographic assessment at 8 weeks of initial investigator-assessed progression the assessment determines continued PD but all the above criteria are met and the investigator considers the participant continues to achieve clinical benefit by continuing treatment, the participant may remain on the trial and continue to receive treatment and monitoring according to the time and events schedule in Section 12.2. Potential for clinical benefit should be balanced by clinical judgment as to whether the participant is clinically deteriorating and unlikely to receive benefit from continued treatment with nivolumab. A second radiographic assessment should be performed within 8 weeks of second investigator-assessed progression to determine whether there has been a decrease in the tumor size or continued PD. If this second 8-week radiographic assessment determines continued PD, then the participant should discontinue therapy and enter the follow-up period.

If the participant undergoes another surgery for presumed tumor progression but pathological findings are consistent with pseudoprogression, the participant will be deemed to not have had tumor progression and may continue treatment with nivolumab after review with the principal investigator.

11.3 Preparation and Administration of Study Drug

Storage and Dispensing

The product storage manager should ensure that the study drug is stored in accordance with the environmental conditions (temperature, light, and humidity) in accordance with the package insert and as per investigator brochure provided by BMS for nivolumab (Opdivo®). If concerns regarding the quality or appearance of the study drug arise, the study drug should not be dispensed and BMS should be contacted immediately.

Nivolumab vials must be stored at a temperature of 2°C to 8°C and should be protected from light and freezing. If stored in a glass front refrigerator, vials should be stored in the carton. Recommended safety measures for preparation and handling of nivolumab include laboratory coats and gloves.

For details on prepared drug storage and use time of nivolumab under room temperature/light and refrigeration, please refer to the nivolumab Investigator Brochure section for “Recommended Storage and Use Conditions” and/or Pharmacy Manual.

Infusion related supplies (eg, IV bags, in-line filters, 0.9% NaCl solution) should be purchased locally.

11.4 Participant Compliance Monitoring

Treatment compliance will be monitored by drug accountability as well as participant’s medical record and CRF.

11.5 Prior and Concomitant Therapy

Prior therapy

Prior treatment with alkylating agents is required inclusion criteria for this study.

Prohibited and/or Restricted Treatments

The following medications are prohibited during the study (unless utilized to treat a drug-related AE):

- Immunosuppressive agents
- Immunosuppressive doses of systemic corticosteroids. Dexamethasone is permitted for anti-edema treatment.
- Any concurrent anti-neoplastic therapy

Other Restrictions and Precautions

Participants with a condition requiring systemic treatment with either corticosteroids (> 10 mg daily prednisone equivalent) or other immunosuppressive medications within 14 days of treatment assignment are excluded. Inhaled or topical steroids, and adrenal replacement steroid doses > 10 mg daily prednisone equivalent, are permitted in the absence of active autoimmune disease.

Participants are permitted the use of topical, ocular, intra-articular, intranasal, and inhalational corticosteroids (with minimal systemic absorption). Adrenal replacement steroid doses > 10 mg daily prednisone are permitted. A brief (less than 3 weeks) course of corticosteroids for prophylaxis (eg, contrast dye allergy) or for treatment of non-autoimmune conditions (eg, delayed-type hypersensitivity reaction caused by a contact allergen) is permitted. Dexamethasone ≤ 4 mg/day or equivalent is permitted for vasogenic brain edema.

11.6 Packaging

OPDIVO® is a sterile, preservative-free, non-pyrogenic, clear to opalescent, colorless to pale-yellow liquid that may contain light (few) particles. OPDIVO® injection for intravenous infusion is supplied in single-dose vials. Cartons of Nivolumab will be provided for this study. Each carton contains: 5 vials of 100mg Nivolumab, 10 mg/mL.

11.7 Blinding of Study Drug

Not applicable

11.8 Receiving, Storage, Dispensing and Return

Receipt of Drug Supplies

Opdivo® (nivolumab) will be shipped to each local research pharmacy.

Study Drug Records

It is the responsibility of the investigator to ensure that a current disposition record of study drug (inventoried and dispensed) is maintained at the study site to include investigational product. Records or logs must comply with applicable regulations and guidelines and should include the following:

- Amount received and placed in storage area
- Amount currently in storage area
- Label identification number or batch number
- Amount dispensed to and returned by each participant, including unique participant identifiers
- Amount transferred to another area/site for dispensing or storage
- Nonstudy disposition (eg, lost, wasted)
- Amount destroyed at study site, if applicable
- Amount returned to BMS
- Retain samples for bioavailability/bioequivalence, if applicable
- Dates and initials of person responsible for IP dispensing/accountability, as per the Delegation of Authority Form.

Dispensing of Study Drug

Regular study drug reconciliation will be performed to document drug assigned, drug consumed, and drug remaining. This reconciliation will be logged on the drug reconciliation form, and signed and dated by the study team. Nivolumab will be dispensed by the research pharmacy to the infusion center team.

Return or Destruction of Study Drug

Return of Study Drug

It is the investigator's responsibility to arrange for disposal of all empty containers, provided that procedures for proper disposal have been established according to applicable federal, state, local, and institutional guidelines and procedures, and provided that appropriate records of disposal are kept.

BMS must be notified of all drug destructions/disposals as detailed below.

Destruction of Study Drug

For this study, study drugs (those supplied by BMS or sourced by the investigator) such as partially used study drug containers, vials and syringes may be destroyed on site.

Columbia University Medical Center
Herbert Irving Comprehensive Cancer Center
Version Date: January 30, 2024

Any unused study drugs can only be destroyed after being inspected and reconciled by the responsible Study Monitor unless study drug containers must be immediately destroyed as required for safety, or to meet local regulations (eg, cytotoxics or biologics).

On-site destruction is allowed provided the following minimal standards are met:

- On-site disposal practices must not expose humans to risks from the drug
- On-site disposal practices and procedures are in agreement with applicable laws and regulations, including any special requirements for controlled or hazardous substances
- Written procedures for on-site disposal are available and followed. The procedures must be filed with the site's standard operating procedures and a copy provided to BMS upon request.
- Records are maintained that allow for traceability of each container, including the date disposed of, quantity disposed, and identification of the person disposing the containers. The method of disposal, ie, incinerator, licensed sanitary landfill, or licensed waste disposal vendor must be documented
- Accountability and disposal records are complete, up-to-date, and available for the Monitor to review throughout the clinical trial period. If conditions for destruction cannot be met, the responsible Study Monitor will make arrangements for return of study drug. It is the investigator's responsibility to arrange for disposal of all empty containers, provided that procedures for proper disposal have been established according to applicable federal, state, local, and institutional guidelines and procedures, and provided that appropriate records of disposal are kept.
- BMS must be notified of all drug destructions.

12 STUDY CALENDAR

Baseline evaluations are to be conducted within 28 days prior to start of protocol therapy. Scans must be done \leq 2 weeks prior to the start of therapy.

12.1 Table 12.1: Screening Assessments

Screening Assessments		
Procedure	Screening Visit	Notes (Screening procedures are to occur within 28 days prior to first dose unless otherwise specified)
Eligibility Assessment		
Informed Consent	X	
Inclusion/Exclusion Criteria	X	All inclusion/exclusion criteria should be assessed at screening
Medical History	X	
Prior Systemic Therapy	X	
Prior Radiation Therapy	X	
Prior Surgery	X	

Columbia University Medical Center
Herbert Irving Comprehensive Cancer Center
Version Date: January 30, 2024

Safety Assessments		
Complete Physical Exam	X	Include neurological exam
Performance Status	X	Karnofsky Performance Status
Vital Signs	X	Temperature, BP, HR
Assessment of Signs and Symptoms	X	Required for the 28 days prior to the first dose
Concomitant Medication Collection	X	Required for the 28 days prior to the first dose
Laboratory Tests	X	CBC with differential, chemistry panel including LDH, AST, ALT, ALP, albumin, TBIL, BUN or serum urea level, uric acid, creatinine, phosphate, Ca, Mg, Na, K, Cl, glucose, amylase, lipase, TSH, T3, Free T4 within 14 days prior to first dose. Hepatitis B surface antigen (HBV sAg) and Hepatitis C antibody (HCV Ab) or HCV Ribonucleic acid (RNA) within 28 days prior to first dose.
Pregnancy Test	X	For WOCBP (Refer to Section 6.3) only and must be done within 24 hours of first dose
Efficacy Assessment		
Radiographic Tumor Assessment: Gadolinium-enhanced MRI of the brain with 2HG MR Spectroscopy	X	To be performed within 14 days of the first dose
Neurologic Assessment in Neuro-Oncology (NANO) Scale	X	
Correlative Assessment		
Archival Tissue	X	Minimum of 20 unstained slides, see laboratory manual for additional details

12.2 Table 12.2: On-treatment procedures

On-treatment Procedures			
Procedure	Cycle 1, Day 1	Cycle 2 and beyond, Day 1	Notes¹:
Safety Assessments			
Targeted Physical Examination	X	X	
Vital Signs	X	X	Temperature, BP, HR
Adverse Events Assessment	-----Assessed Continuously-----		Assessed using NCI CTCAE v. 4.03
Review of Concomitant Medications	X	X	
Physical Measurements	X	X	Includes weight
Karnofsky Status	X	X	
Laboratory Tests		X	To be done within 72 hours of dosing and

Columbia University Medical Center
Herbert Irving Comprehensive Cancer Center
Version Date: January 30, 2024

			
include: CBC with differential, uric acid, BUN or serum urea level, creatinine, Mg, Ca, K, Cl, Na, amylase, lipase, glucose, phosphate, AST, ALT, TBILI, ALP, albumin, LDH
 
Cycle 1 Day 1: Laboratory tests do not need to be repeated if performed within 14 days of the first dose

Thyroid function testing		See note	Thyroid function testing (TSH with reflexive T3 and fT4) is to be done every 3 infusions starting on C3D1 followed by C6D1 etc. for patients receiving nivolumab at 240mg Q2W, then every 2 infusions starting at C9D1 followed by C11D1 etc. for participants receiving nivolumab at 480mg Q4W (every other infusions)
Pregnancy Test (WOCBP only)	X	X	Serum or urine pregnancy test must be performed within 24 hours of C1D1 and must also be performed within 24 hours of all subsequent cycles (i.e. C2D1, C3D1, C4D1, etc.)
Efficacy Assessments			
Radiographic Tumor Assessment: Gadolinium enhanced MRI of the brain with 2HG MR spectroscopy		See note	Tumor assessments will occur every 8 weeks (\pm 2 weeks) from C1D1 for up to 2 years while the patient is on treatment or until disease progression
Neurologic Assessment in Neuro-Oncology (NANO) Scale		See note	NANO every 8 weeks (\pm 7 days of each MRI)
Clinical Drug Supplies			
Administer Nivolumab	X	X	Participants should receive Nivolumab at a dose of 240mg as a 30-minute infusion on Day 1 of each treatment cycle for 8 cycles until Q4W dosing begins. Participants may be dosed

Columbia University Medical Center
Herbert Irving Comprehensive Cancer Center
Version Date: January 30, 2024

			no less than 12 days from the previous dose. For Q2W dosing cycles, participants may be dosed within a ± 2 day window. Beginning with Cycle 9, participants should receive Nivolumab at a dose of 480mg as a 30-minute infusion every 4 weeks (± 3 days) for a maximum 2 years of total treatment, or until PD, unacceptable toxicity, or withdrawal of consent.
Correlative Assessments			
Blood for Whole Exome Sequencing	X		Blood sample can be drawn on C1D1 or at anytime while the patient is on study, see laboratory manual for additional details
¹ All windows proposed are calendar days. Procedures must be done within 72h prior to dosing unless otherwise specified. Cycle duration is 2 weeks until 8 doses have been completed; subsequent cycles are 4 weeks in duration			

12.3 Table 12.3: Follow up Assessments

Procedure	Follow up Assessments		
	Follow ups, Visit 1 and Visit 2 (X01 & X02)*	Survival Assessments	Notes
Safety Assessments			
Targeted Physical Examination	X		
Adverse events assessment	X		Assessed using NCI CTCAE v. 4.03. Adverse events must be collected for at least 100 days following the last dose of study treatment and at both X01 and X02 follow-up visits.,
Laboratory tests	X		Required for X01: CBC with differential, uric acid, BUN or serum urea level, creatinine, Ca, Mg, K, Cl, Na, amylase, lipase, glucose, phosphate, AST, ALT, TBIL, ALP, albumin, LDH. Panel should also be performed at X02 if X01 results were abnormal and clinically

Columbia University Medical Center
Herbert Irving Comprehensive Cancer Center
Version Date: January 30, 2024

			signficiant
Pregnancy Test (WOCBP only)	X		Serum or urine pregnancy test at X01 only
Efficacy Assessments			
Radiographic tumor assessment: Gadolinium-enhanced MRI of the brain	See note	X	If the subject had disease progression on -study then no additional tumor assessments are required. If not, tumor assessments will continue to occur as per standard of care, however, RANO assessments must be completed and documented until disease progression or start or subsequent anti-cancer therapy (whichever occurs first). 2HG is not required for scans during follow-up.
Participant Status			
Participant Status	X	X	
Survival follow up visits are expected to occur every 3 months after X02; May be accomplished by visit or phone contact to update survival information and assess subsequent anti-cancer therapy.
 
Principal Investigator may request that survival data be collected on all treated participants outside of the 3-month specified window. At the time of this request, each participant will be contacted to determine their survival status unless the participant has withdrawn consent for all contact.

Subsequent Anti-Cancer Therapy	X	X	This assessment coincides with the participant status assessment performed at survival follow up vists every 3 months after X02.

* Follow-up visit 1 (X01) = 35 days (+/- 7 days) from the last dose or coincide with the date of discontinuation (+/- 7 days) if date of discontinuation is greater than 42 days after last dose. Follow-up visit 2 (X02) = 80 days (+/- 7 days) from follow-up visit 1. Additionally, if the patient starts a subsequent anti-cancer therapy prior to X01 and/or X02, then they do not need to be completed. Survival follow-up visits should continue for all patients regardless of whether they start subsequent anti-cancer therapy.

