5.6 Safety Assessments

At screening, a medical history will be obtained to capture relevant underlying conditions. The screening examinations should include weight, height, Karnofsky status, blood pressure (BP), heart rate (HR), and temperature.

Screening local laboratory assessments should be done within 14 days prior to treatment assignment and are to include: CBC with differential, chemistry panel including LFTs (ALT, AST, TBILI, ALP), amylase, lipase, uric acid, BUN or serum urea level, creatinine, Ca, Na, K, Cl, Mg, albumin, phosphate, LDH, glucose, and thyroid panel including TSH, T3, and free T4.

Pregnancy tests for WOCBP must be performed within 24 hours prior to the initial administration of study drug and every cycle thereafter.

The following screening local laboratory assessments should be done within 28 days prior to treatment: Hepatitis B and C testing (HBV sAg and HCV Ab or HCV RNA).

While on-study the following local laboratory assessments are to be done within 3 calendar days prior to each dose: CBC with differential, LFTs (ALT, AST, TBILI, ALP), BUN or serum urea level, creatinine, Ca, Mg, Na, K, Cl, phosphate, LDH, uric acid, amylase, lipase, albumin, glucose.

Columbia University Medical Center
Herbert Irving Comprehensive Cancer Center
Version Date: January 30, 2024

Thyroid function testing (TSH with reflexive T3 and fT4) is to be done every 3 infusions starting on C3D1 followed by C6D1 etc. for participants receiving nivolumab at 240 mg Q2W, then every 2 infusions starting at C9D1 followed by C11D1 etc. for participants receiving nivolumab at 480 mg Q4W (every other infusion).

On treatment pregnancy tests should be performed as per the schedule in the time and events table (Table 12.1-2).

Participants will be evaluated for safety if they have received any study drug. Toxicity assessments will be continuous during the treatment phase as well as during the first 2 safety follow-up visits. Once participants reach the survival follow-up phase, either in-person visits or documented telephone calls to assess the participant's status are acceptable.

Adverse events and laboratory values will be graded according to the NCI CTCAE version 4.03.

The start and stop time of the study therapy infusions and any interruptions or infusion rate reductions should be documented.

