10.4 Adverse Event Reporting Period

The study period during which adverse events must be reported starts on the day of consent and continues for at least 100 days following the last administration of study drug.

Baseline/Preexisting Condition

A baseline/preexisting condition is one that is present at the start of the study. A preexisting condition should be recorded as an adverse event if the frequency, intensity, or if the character of the condition worsens during the study period.

General Physical Examination Findings

At screening, any clinically significant abnormality should be recorded as a preexisting condition. At the end of the study, any new clinically significant findings/abnormalities that meet the definition of an adverse event must also be recorded and documented as an adverse event.

Post-study Adverse Event

All unresolved adverse events should be followed by the investigator until the events are resolved, the participant is lost to follow-up, or the adverse event is otherwise explained. At the last scheduled visit, the investigator should instruct each participant to report any subsequent event(s) that the participant, or the participant's personal physician, believes might reasonably be related to participation in this study.

Abnormal Laboratory Values

A clinical laboratory abnormality should be documented as an adverse event if any one of the following conditions is met:

- The laboratory abnormality is not otherwise refuted by a repeat test to confirm the abnormality
- The abnormality suggests a disease and/or organ toxicity

- The abnormality is of a degree that requires active management or meets criteria for a SAE (e.g., change of dose, discontinuation of the drug, more frequent follow-up assessments, further diagnostic investigation, etc.).

Hospitalization, Prolonged Hospitalization or Surgery

Any adverse event that results in hospitalization or prolonged hospitalization should be documented and reported as a serious adverse event unless specifically instructed otherwise in this protocol. Any condition responsible for surgery should be documented as an adverse event if the condition meets the criteria for an adverse event.

Neither the condition, hospitalization, prolonged hospitalization, nor surgery are reported as an adverse event in the following circumstances:

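### The Table 12.3 footnote waives safety visits after new therapy starts, while the 100-day adverse-event duty stays in force with no scheduled contact to deliver it

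*Combined protocol and SAP*

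**What the plan says.** Section 12.3 schedules two off-drug safety visits: "Follow-up visit 1 (X01) = 35 days (+/- 7 days) from the last dose" and "Follow-up visit 2 (X02) = 80 days (+/- 7 days) from follow-up visit 1". X01 moves to the date of discontinuation "if date of discontinuation is greater than 42 days after last dose".

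The adverse-event row of Table 12.3 requires collection for at least 100 days after the last dose and "at both X01 and X02 follow-up visits". It states no exception. The footnote to the same table then says that "if the patient starts a subsequent anti-cancer therapy prior to X01 and/or X02, then they do not need to be completed", and keeps survival follow-up for everyone.

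The 100-day period also appears in Section 10.2 (non-serious events), in Section 10.4, where the reporting period "continues for at least 100 days following the last administration of study drug", and in Section 10.6 (serious events, whatever their relation to study drug). None of these ends the period when new therapy begins. Section 5.6 ties off-drug toxicity assessment to the same two visits: "Toxicity assessments will be continuous during the treatment phase as well as during the first 2 safety follow-up visits".

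For later contacts, Table 12.3 says "Survival follow up visits are expected to occur every 3 months after X02". Participant status and subsequent therapy are marked for these contacts; adverse-event assessment is not.

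**The concern.** A site cannot follow both the adverse-event row and the footnote for a participant who moves to other therapy early. If it follows the footnote, the 100-day duty remains but the schedule no longer contains the visits that carry it out.

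Sections 5.1 and 15.1 describe the trial as estimating safety as well as efficacy. Nivolumab can cause immune-mediated events, and some may appear after the last dose. If off-drug assessment depends on how soon a participant changes therapy, late events are ascertained unevenly, and the participants with the least coverage are not a random subset. With 37 participants planned, one participant with a missed event type shifts that event's reported rate by 1/37 = 2.7 percentage points.

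**Working it through.** **Inputs.** X01 is 35 ± 7 days after the last dose and X02 is 80 ± 7 days after X01 (footnote to Table 12.3). The collection period is at least 100 days (Table 12.3 and Sections 10.2, 10.4 and 10.6). Survival contacts run every 3 months after X02 (Table 12.3 and Section 6.9).

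**Step 1: does the schedule cover the window when nothing is waived?**
- X01: 35 − 7 = day 28 to 35 + 7 = day 42.
- X02: earliest 28 + 73 = day 101; nominal 35 + 80 = day 115; latest 42 + 87 = day 129.

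The earliest X02 falls just after day 100. X01 is therefore the only scheduled safety visit inside the window, and X02 closes the window by looking back over what remains. The two visits together deliver the plan's 100 days.

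If discontinuation comes more than 42 days after the last dose, both visits move later (X01 no earlier than 43 − 7 = day 36, X02 no earlier than 36 + 73 = day 109). The rest of this check uses the default timing.

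**Step 2: what remains after the waiver?**

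| New therapy starts | X01 | X02 | Safety visits in days 0–100 | Part of the window with no later scheduled look-back |
|---|---|---|---|---|
| Never, or after X02 | done | done | 1, then X02 closes the window | none |
| Between X01 and X02 | done | waived | 1 | 100 − 42 = 58 to 100 − 28 = 72 days |
| Before X01 | waived | waived | 0 | all of the off-drug window |

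**Step 3: does another scheduled contact fill the gap?**
- Follow-up scans stop at progression or at the start of new therapy, whichever comes first (Section 5.6).
- Survival contacts have no adverse-event assessment marked, and their clock starts at a visit that may not take place. If the clock is assumed to run from the nominal X02 date and 3 months is taken as 91 days, the first contact falls on 115 + 91 = day 206 (101 + 91 = 192 to 129 + 91 = 220).
- Sections 5.6, 10.2 and 10.4 continue the follow-up of toxicities already known. They schedule nothing to detect new ones.
- Section 6.9 allows only withdrawal of consent, or loss of the ability to consent freely, as exceptions to follow-up. It does not list new therapy, although it sends the reader to Section 12.3, where the footnote sits.

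**The case against.** The strongest defence is that the footnote is a deliberate exception. It hangs on the column heading for X01 and X02, Section 6.9 points to that table, and attribution is harder once another therapy has begun. This could justify dropping examinations or laboratory tests. It does not explain how adverse events are to be collected to day 100, because that duty is kept, and Section 10.6 requires serious events to be reported whether or not they are related.

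Several stronger readings are tempting, and the documents do not support them:
- **Everyone who starts new therapy loses both visits.** This holds only for a start before X01. After X01 only X02 is lost, and X02 lies outside the strict 100 days.
- **Events would be recorded only if volunteered.** Section 10.5 requires specific questioning about adverse events at every contact, which includes survival calls. The gap is that no contact is scheduled in time.
- **The participant has no contact of any kind from the last dose.** Assessment is continuous on treatment, and the evaluation that leads to stopping can itself fall after the last dose.
- **Most participants are affected.** The documents give no rate of early new therapy. Sections 3 and 4.3 describe limited options and no accepted standard of care at recurrence, and Section 11.2 permits treatment beyond initial progression.
- **The safety denominator changes.** All treated participants stay evaluable for toxicity (Sections 13.1.1 and 15.7). What varies is ascertainment.
- **The efficacy results are compromised.** Nothing in the waiver changes how response, PFS, OS or duration of response is defined. The undefined anchor affects when survival contacts happen, while the footnote itself keeps survival follow-up for all.

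**Conclusion.** The point holds as an internal conflict and a gap in delivery. The footnote disagrees with the adverse-event row of its own table, and it leaves the 100-day duty without a scheduled means of being met. For a start of new therapy before X01 (day 28 to 42), no safety visit is scheduled in the window. For a start between X01 and X02, the last 58 to 72 days have no scheduled look-back. In both cases survival follow-up has no defined anchor.

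These figures rest on the default visit windows. The day-206 figure also assumes a clock running from the nominal X02 date and a 91-day interval. The number of participants affected and the number of events missed cannot be stated from the documents. The matter should be corrected because a stated safety requirement depends on it and the correction is small. It does not threaten the primary analysis.

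**What to change.** - Reconcile the Table 12.3 footnote with the adverse-event row of that table and with Sections 5.6, 6.9, 10.2, 10.4 and 10.6.
- Whatever is decided about examinations and laboratory tests, state that when X01 and/or X02 is waived, collection of adverse and serious adverse event data continues to at least day 100 by visit or telephone. Section 5.6 and Table 12.3 already accept telephone contact for survival follow-up.
- Report off-drug events separately before and after the start date of new therapy. Subsequent therapy is already a row in Table 12.3, and Section 15.5 needs its start for PFS censoring, so this should add little data collection.
- Define what survival follow-up is timed from when X02 does not take place.

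The cost is an edited footnote with matching cross-references, and up to two short telephone contacts per affected participant.
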